8.2.7. ECOG Performance Status

ECOG performance status ([Appendix 7](#)) should be evaluated by the investigator by direct questioning of the subject at screening and at timepoints delineated in the SoA ([Table 1](#)).

8.2.8. Ophthalmologic Examinations

Ophthalmic examination if clinically indicated (ie, if subject is at high risk for RVO, RPED, and/or central serous retinopathy because of predisposing factors [uncontrolled glaucoma or ocular hypertension, uncontrolled diabetes mellitus, hyperviscosity, or hypercoagulability syndromes]), including full fundoscopic examination and OCT should be performed at Screening by an ophthalmologist as described in the SoA ([Table 1](#)). Additional examinations should be performed during study treatment as clinically indicated.

8.3. Adverse Events and Serious Adverse Events

The definitions of AE and SAE can be found in [Appendix 3](#).

AEs will be reported by the subject (or, when appropriate, by a caregiver, surrogate, or the subject's legally authorized representative).

The investigator and any qualified designees are responsible for detecting, documenting, and recording events that meet the definition of an AE or SAE and remain responsible for following AEs that are serious, considered related to the study treatment or study procedures, or that caused the subject to discontinue the study treatment (see [Section 7](#)).

8.3.1. Time Period and Frequency for Collecting AE and SAE Information

Monitoring and recording of AEs and SAEs will be conducted throughout the study. After the signing of the ICF, but prior to initiation of study treatment, only SAEs caused by a protocol-mandated treatment will be collected (eg, SAEs related to invasive procedures, such as biopsies or medication washout). Any medical occurrence that begins before the start of study treatment but after obtaining informed consent, and which is not considered an SAE caused by a protocol-mandated treatment, will be recorded on the Medical History/Current Medical Conditions Section of the eCRF rather than the AE section.

All AEs and SAEs will be collected from the start of treatment until 30 days after the last dose, or upon initiation of alternative cancer treatment, whichever occurs first. After this period, investigators should report only SAEs that are thought to be related to RMC-4630 and/or sotorasib.

Any SAE that is determined to be study-treatment related (possibly, probably, or definitely related) will be followed to resolution or stabilization, until it is determined to be irreversible by the investigator, the subject is lost to follow-up, or it has been determined that the study treatment is not the cause of the AE/SAE, whichever occurs first. After this period, investigators should report only SAEs that are thought to be related to RMC-4630 and/or sotorasib.

All SAEs will be recorded and reported to the Sponsor or designee within 24 hours of investigator awareness, as indicated in [Appendix 3](#). The investigator will submit any updated SAE data to the Sponsor within 24 hours of it being available. During the Extended-Use phase of the study, only SAEs (irrespective of causality) and related AEs will be reported in the EDC. All SAEs will also be reported on the SAE Report Form.

8.3.2. Method of Detecting AEs and SAEs

The method of recording, evaluating, and assessing causality of AE and SAE and the procedures for completing and transmitting SAE reports are provided in [Appendix 3](#).

Care will be taken to not introduce bias when detecting AEs and/or SAEs. Open-ended and nonleading verbal questioning of the subject is the preferred method to inquire about AE occurrences.

8.3.3. Follow-Up of AEs and SAEs

After the initial AE/SAE report, the investigator is required to proactively follow each subject at subsequent visits/contacts through the last study visit. All AEs (regardless of relationship to study treatment) and SAEs determined not to be study-treatment related (ie, not related and unlikely related) will be followed through the last study visit and be noted as “continuing” if not resolved at this visit.

All SAEs considered study-treatment related (possibly, probably, or definitely related) will be followed until resolution, stabilization, is determined to be irreversible by the investigator, the subject is lost to follow-up (as defined in [Section 7.3](#)), or it has been determined that the study

treatment is not the cause of the AE/SAE, whichever occurs first. The investigator will submit any updated SAE data to the Sponsor within 24 hours of it being available. During the Extended-Use phase of the study, only SAEs (irrespective of causality) and related AEs will be reported in the EDC. All SAEs will also be reported on the SAE Report Form. Reporting of AEs/SAEs will end after the subject initiates alternative cancer treatment.

Further information on follow-up procedures is given in [Appendix 3](#).

8.3.4. Regulatory Reporting Requirements for SAEs

- Prompt notification (ie, within 24 hours of becoming aware of the event) by the investigator to the Sponsor of a SAE is essential so that legal obligations and ethical responsibilities toward the safety of subjects and the safety of a study treatment under clinical investigation are met.
- The Sponsor has a legal responsibility to expeditiously notify both the local regulatory authority and other regulatory agencies about the safety of a study treatment under clinical investigation. The Sponsor will comply with country specific regulatory requirements relating to safety reporting to the regulatory authority, central IRBs/IECs, and investigators.
- The Sponsor will prepare investigator safety reports for suspected unexpected serious adverse reactions (SUSARs), according to local regulatory and local IRB/IEC requirements and Sponsor policy, and forward them to investigators, as necessary within 7 calendar days for Fatal and Life-Threatening SUSARs and 15 calendar days for all other SUSARs.
- An investigator who receives an investigator safety report describing a SAE or other specific safety information (eg, summary or listing of SAEs) from the Sponsor will review and then file it along with the RMC-4630 IB and will notify the IRB/IEC, if appropriate, according to local requirements.
- The Sponsor will regularly monitor reporting of SUSARs through compliance metrics and corrective and preventative actions to ensure that all recipients receive SUSAR reports in a timely manner.
- During the Extended-Use phase of the study, only SAEs (irrespective of causality) and related AEs will be reported in the EDC. All SAEs will also be reported on the SAE Report Form.

8.3.5. Pregnancy

- Details of all pregnancies in female subjects and female partners of male subjects who become pregnant will be collected after the start of study treatment and will be followed to determine the outcome of the pregnancy.
- If a pregnancy is reported, the investigator should inform the Sponsor within 24 hours of learning of the pregnancy and should follow the procedures outlined in [Appendix 4](#).
- Abnormal pregnancy outcomes (eg, spontaneous abortion, fetal death, stillbirth, congenital anomalies, ectopic pregnancy) are considered SAEs.

- Pregnancy reporting as detailed above will continue during the Extended-Use phase of the study and should be reported to Drug Safety on the SAE report form.

8.3.6. Committees

8.3.6.1. Dose Committee

The Dose Committee is a study specific committee, composed of Sponsor representatives and investigators. Additional details regarding memberships, roles, and responsibilities are provided in the Dose Committee Charter.

The Dose Committee will evaluate the safety data for the safety lead-in portion of the study. The combination dose for the expansion phase of the study will be decided by the Sponsor after taking into consideration the totality of data from both CodeBreaK 101C and the cumulative data from this study. The Sponsor may proceed directly to dose expansion in this study without completing the safety run-in period based on review of available data.

8.3.6.2. ISMC

The ISMC consists of representatives from the Sponsor and the designated CROs, as outlined in the ISMC Charter. The ISMC will review emergent safety data as per the ISMC charter from the RMC-4630 program after approximately every 3 months or after the first 6 subjects have completed 2 cycles in this study, whichever is earlier. The ISMC may also perform emergent ad hoc reviews of the safety data for all subjects during the study. Subsequently the committee will review data approximately every 3 months. The committee may adjust the timing of the review from the defined schedule, depending on the rate of enrollment. The committee will consist of the medical monitor, and a biostatistician. Relevant findings from the safety data reviews will be discussed with the study investigators. Based on the ongoing safety assessments, the committee may recommend changes in dosing regimen or other alterations to study procedures. The medical monitor may convene a meeting sooner should any concerns arise from review of data or from the investigators.

8.4. Dose Limiting Toxicity Criteria

Potential DLTs are defined as all AEs specified below that occur during the first cycle of study treatment and that are considered by the investigator to be related to RMC-4630 and/or sotorasib.

DLT criteria are outlined below as follows:

- An AE that results in permanent discontinuation of RMC-4630 or sotorasib
- An AE that results in a delay of > 2 weeks in the start of Cycle 2
- Febrile neutropenia
- Grade 4 neutropenia of any duration
- Grade 3 neutropenia lasting >7 days
- Grade 3 thrombocytopenia with Grade ≥ 2 bleeding
- Grade 4 thrombocytopenia
- Grade 4 anemia
- Grade ≥ 4 vomiting and diarrhea

- Grade 3 vomiting or diarrhea lasting >3 days despite optimal medical support
- Grade ≥ 3 nausea lasting 3 days or more, despite optimal medical support
- Grade ≥ 3 rash lasting 3 days or more despite optimal medical support
- Grade 3 AST or ALT elevation lasting >5 days or Grade ≥ 4 AST or ALT elevation of any duration
- Grade ≥ 3 bilirubin elevation
- Grade ≥ 3 QTc prolongation
- Retinal vein occlusion
- Any other Grade ≥ 3 AE with the following exceptions:
 - Grade 3 Fatigue lasting 7 days or less
 - Asymptomatic Grade 3 electrolyte abnormalities that last <72 hours, are not clinically complicated, and resolve spontaneously or respond to medical interventions
 - Grade 3 amylase or lipase that is not associated with symptoms or clinical manifestations of pancreatitis
 - Other select laboratory abnormalities that do not appear to be clinically relevant or harmful to the subject and/or can be corrected with replacement or modifications (eg, Grade 3 lymphopenia, Grade 3 hypoalbuminemia)
- Any subject meeting the criteria for a Hy's Law case (ie, severe DILI) will be considered a DLT. A Hy's Law case is defined as the following: AST or ALT values of $\geq 3 \times$ ULN, AND total bilirubin $>2 \times$ ULN or INR >1.5 in the absence of cholestasis and other causes (eg, viral hepatitis, other preexisting or acute liver disease, or another drug capable of the observed injury), to explain the observed liver related laboratory abnormalities.

If a subject experiences a DLT during the DLT evaluation period during Cycle 1 of the safety run-in period, sotorasib and/or RMC-4630 treatment should be modified according to [Table 6](#) and [Table 7](#).

8.5. Treatment of Overdose

For this study, any dose of RMC-4630 or sotorasib that is greater than the intended dose per administration or 2 administrations at the intended dose or more of sotorasib within <12 hours (QD dosing) or 2 administrations of RMC-4630 <12 hours apart (BIW D1, D2 dosing) will be considered an overdose. There is no clinical experience with an overdose of RMC-4630 in human clinical trials. No experiments have been performed to determine whether the effects of an overdose can be reversed, and there are no known antidotes.

Revolution Medicines does not recommend specific treatment for an overdose. The individual should be monitored clinically, and supportive care should be undertaken as clinically indicated.

In the event of an overdose, the investigator should:

1. Halt the dispensation and administration of the involved medication. The investigator may also hold the second medication based on his/her clinical judgement.
2. Contact the Medical Monitor immediately.
3. Closely monitor the subject for any AE/SAE, ECG, and laboratory abnormalities (blood glucose, liver function tests, creatinine, blood urea nitrogen (BUN), creatine phosphokinase (CPK), and complete blood count) until RMC-4630 and/or sotorasib can no longer be detected systemically.
4. Obtain a plasma sample for PK analysis within 1 to 2 days from the date of the last dose of study intervention if requested by the Medical Monitor (determined on a case-by-case basis). Note, the PK sample collection applies to the main protocol only and not the Extended-Use phase.
5. Document the quantity as well as the duration of the overdose in the eCRF.
6. Decisions regarding resumption of study treatment will be made by the investigator in consultation with the Sponsor's Medical Monitor based on clinical evaluation of the subject.

8.6. Pharmacokinetics

Plasma samples will be obtained for PK analysis of RMC-4630 and sotorasib as outlined in the SoA and [\(Table 2\)](#). Peripheral blood samples will be collected within C1 for sparse PK testing, and additional PK evaluations will continue to be obtained through C4 and every 3 cycles afterward up to Cycle 16. Note, PK sample collection applies to the main protocol only and not the Extended-Use phase.

PK parameters (ie, approximate peak and trough concentrations) of RMC-4630 and sotorasib will be assessed for each evaluable subject:

- Whole blood samples of approximately 3.0 mL will be drawn and processed into plasma for measurement of plasma RMC4630 and sotorasib concentrations as specified in the -SoA and [Table 2](#). Instructions for the collection and handling of biological samples will be provided by the Sponsor. The actual date and time (24-hour clock) of each sample will be recorded.
- Samples will be used to evaluate the PKs of RMC-4630 and sotorasib. Each plasma sample will be divided into 4 aliquots (2 each for primary and backup). Samples collected for analyses of plasma RMC-4630 and sotorasib concentrations may also be used for exploratory analysis, such as analysis of plasma RMC-4630 and sotorasib metabolites.

Genetic analyses will not be performed on these plasma samples. Subject confidentiality must be maintained. Any changes in the timing or addition of time points for any planned study assessments must be documented and approved by the relevant study team member and then archived in the Sponsor and site study files but will not constitute a protocol amendment. The IRB/IEC will be informed of any safety issues that require alteration of the safety monitoring scheme or amendment of the ICF. There will be no PK sample collection in the Extended-Use phase of the study.

8.7. Tumor Genetics

Enrollment will be determined based on genotypic/histotypic strata mentioned in [Section 5.1](#) (Inclusion Criteria). Specific mutations are also defined in [Appendix 9](#). Eligible mutations will be based on prior genotyping results using a clinically validated or qualified test. This test may have been performed on either tumor tissue or ctDNA samples. Sites must provide the Sponsor with the report. Archival tumor tissue will be collected for central laboratory testing. Details on processes for collection and shipment can be found in the laboratory manual. Fresh pretreatment biopsies will be mandatory for subjects who do not have available archival specimen tissue preferably from within 3 years, unless the investigator determines that the tumor site is not amenable to biopsy or poses a significant risk to the subject's safety. Subjects who neither have archival tumor tissue samples nor can provide fresh pretreatment biopsies may still be eligible to participate in the study with agreement from the Sponsor Medical Monitor. The Sponsor will evaluate this requirement on a case-by-case basis. In the event of a discrepancy between the local and central testing results for the eligibility defining mutation, the subject will remain on study. For data analysis purposes, results from the central laboratory will supersede those of the local laboratory.

Information regarding genetic research is provided in [Appendix 5](#).

8.8. Other Biomarkers

Archival tumor samples will be collected for all subjects. These samples will be used to confirm mutations identified on the genomic report provided at enrollment. Archival samples will also be used to assess and evaluate potential markers of response to RMC-4630 and sotorasib combination therapy, including but not limited to deoxyribonucleic acid (DNA), ribonucleic acid (RNA), and protein expression. If tumor tissue allows, the remaining archival tumor samples may be stored for future development of companion diagnostic.

Blood samples will be drawn as outlined in the SoA ([Table 1](#)) and [Table 2](#) from every subject in order to extract and analyze ctDNA to assess and evaluate potential peripheral biomarkers of response to sotorasib and RMC-4630. Samples may be analyzed retrospectively.

Note, biomarker sample collection applies to the main protocol only and not the Extended-Use phase.

9. STATISTICAL CONSIDERATIONS

This is a Phase 2 multicenter, open-label study evaluating the efficacy, safety, tolerability, and PK of RMC-4630 in combination with sotorasib in subjects with *KRAS^{G12C}* mutant locally advanced or metastatic NSCLC after failure of prior standard therapy. Descriptive statistics will be used to summarize baseline demographic and disease characteristics, treatment administration, efficacy, and safety outcomes, and PK parameters.

Descriptive summaries of discrete data will present the number of study subjects and the incidence as a frequency and as a percentage. Descriptive summaries of continuous data will present the group mean, standard deviation, median, minimum, maximum, and sample size.

A final analysis will be performed at the EOS as defined in [Section 4.4](#).

9.1. Statistical Hypotheses

No formal statistical hypothesis will be tested.

9.2. Sample Size Determination

Up to a total of [REDACTED] subjects will be enrolled into this study. Approximately [REDACTED] subjects will be enrolled during the safety run-in portion of the study. Initially, up to [REDACTED] will be enrolled and treated at the dose of [REDACTED] of each week in a 21-day cycle in combination with sotorasib at 960 mg QD. An additional [REDACTED] may be enrolled to receive RMC-4630 [REDACTED] of each week in a 21-day cycle in combination with sotorasib at 960 mg QD, if a decision is made to increase the RMC-4630 dose from [REDACTED] mg. After completion of the safety run-in (DLT clearance) of both dose levels, additional subjects may be enrolled for the purpose of dose optimization to inform the selection of the final expansion dose. Expansion may commence as soon as the final expansion dose has been selected. Approximately [REDACTED] will be enrolled for dose optimization and dose expansion.

With a total sample size of [REDACTED], the probability of observing at least 1 AE with an incidence rate of 5% is at least 90%.

The ORR will be reported by dose level pooling subjects from safety run-in and dose optimization (if applicable) and expansion. It's anticipated that approximately [REDACTED] subjects will be treated at the final expansion dose depending on the actual number of subjects enrolled during safety run-in and/or dose optimization. For the final expansion dose, with [REDACTED] the lower bound of the one-sided 80% exact CI will be above 33.7% and 37.3% respectively if the observed response rate is 45%.

The mutational status of each subject and, thus, placement into Cohort 1 or 2 (see [Section 4.1](#)) will be determined based on the historic genomic reports and later might be adjusted based on ctDNA analysis results collected at baseline. Therefore, the sample size for one or both cohorts will depend on the distribution of mutational status.

9.3. Populations for Analyses

For purposes of analysis, the following populations are defined in [Table 8](#).

Table 8: Population Definitions

Population	Description
Treated	All subjects who take at least 1 dose of study treatment
Evaluable	DLT-evaluable: All subjects in the safety population who have received at least 80% of planned dose of sotorasib and at least 4 of 6 doses of RMC-4630 in Cycle 1 and have been observed for safety assessments for the full 21 days of the DLT evaluation period. Subjects who experience a DLT within the DLT period will be considered DLT evaluable regardless of the amount of study treatment received or completion of the observation period. Evaluable for efficacy: All subjects with measurable disease at baseline, who take at least 1 dose of study treatment and (1) undergo 1 post-baseline response assessment or (2) who die or (3) had clinical progression prior to the first post-baseline response assessment.

Abbreviations: DLT = dose-limiting toxicity.

9.4. Statistical Analyses

The statistical analysis plan will be developed and finalized before database lock. This section is a summary of the planned statistical analyses of the primary and secondary endpoints.

9.4.1. Efficacy Analyses

The statistical analysis plan will be developed and finalized before database lock. Below is a summary of the planned statistical analyses.

Unless otherwise specified, efficacy analyses will be based on the efficacy-evaluable population and will be summarized by the initial combination dose level. Efficacy analyses will be presented for Cohort 1 and Cohort 2 separately, and for the overall study population.

The primary efficacy endpoint is ORR, defined as the proportion of subjects who achieve a CR or PR per RECIST v1.1. The estimated proportion and the corresponding 95% two-sided exact CI using the Clopper-Pearson method will be derived for ORR.

Secondary efficacy endpoints and analyses include the following:

- DCR is defined as the proportion of subjects who achieve a CR or PR or SD per RECIST v1.1. DCR will be analyzed similarly as ORR.
- DOR is defined as the interval from the first documentation of CR or PR to first documentation of definitive disease progression or death due to any cause, whichever occurs first. Subjects who are still alive and free from progression at the time of the data cutoff date, are lost to follow-up, have discontinued from the study, or have initiated subsequent anticancer therapy will be censored at the last adequate tumor assessment. Subjects who never achieve a response (PR or better) will be excluded from the analysis of DOR.
- PFS is defined as the interval from the first dose of study treatment to documented disease progression per RECIST v1.1 or death due to any cause, whichever occurs first. Subjects who are still alive and free from progression at the time of the data cutoff date, are lost to follow-up, have discontinued from the study, or who have initiated subsequent anticancer therapy will be censored at the last adequate tumor assessment. PFS will be summarized for the all-treated population.

- Overall survival (OS) is defined as the interval from the first dose of study treatment to death due to any cause. Subjects who are not known to have died will be censored at the last known alive date. OS will be summarized on the all-treated population.

The Kaplan-Meier method will be used to estimate DOR, PFS and OS curves and corresponding quartiles. The Kaplan-Meier median will be calculated with a two-sided 95% CI.

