This statistical analysis plan (SAP) has been developed after review of the clinical study protocol RMC4630-03 (Original Protocol Version 1.0 dated 21 June 2021; Version 2.0 22 July 2021, Version 3.0 21 March 2022; Version 4.0 21 November 2022 and electronic case report form (eCRF).

This SAP describes the planned statistical methods for evaluating the efficacy, safety, tolerability, and PK of RMC-4630 in combination with sotorasib data for this study. Additional details of variable definitions are included in the supplemental Standard Programming Specification document. The planned table, figure, and listing (TFL) to be presented in the clinical study report (CSR) is provided in the accompanying TFL shells document.

This SAP supersedes any statistical considerations identified in the protocol; where considerations are substantially different, they will be so identified. If additional analyses are required to supplement the planned analyses described in this SAP, they may be performed and will be identified accordingly in the CSR.

This SAP is written with consideration of the recommendations outlined in the International Conference on Harmonization (ICH) E3 guideline Structure and Content of Clinical Study Reports, ICH E8 guideline General Considerations for Clinical Trials, and ICH E9 guideline Statistical Principles for Clinical Trials.

The document history is presented in [Appendix A](#).

2. Protocol Details

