7.6 Efficacy Analyses

The efficacy endpoints of ORR, DCR, and DOR will be based on the treated population, and will be summarized by the initial combination dose level. As supportive analyses, these efficacy endpoints will also be summarized for the efficacy-evaluable population. PFS and OS will be summarized on the all-treated population. Efficacy analyses will also be presented by Cohort 1 and Cohort 2 at the expansion dose level.

Handling of Missing Efficacy Data

- For analyses of binary endpoints, subjects among the analysis population who have not achieved the outcome of interest by the time of analysis will be considered a non-responder for the analysis.
- For time to event endpoints, subjects without post-baseline assessments will be censored at the date of the first dose of study drug.

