7.9 Exploratory Analyses

Biomarker exploratory analyses may be described in a separate analysis plan and may be summarized in a report separate from the clinical study report.

8. Interim Analyses

No formal interim analysis will be conducted. However, as this is an open-label study, several analyses may be conducted at specific points during the study as well as at the end of the study.

9. Deviations from Statistical Analysis Plan

Any deviations from this statistical plan will be described and justified in the final clinical study report.

10. Significant Changes from the Protocol-specified Analyses

There have been no other changes in analyses from those defined in the protocol.

11. References

- 3 ICH. Statistical Principles for Clinical Trials, Guideline E9, 1998. Available at https://www.ich.org/fileadmin/Public_Web_Site/ICH_Products/Guidelines/Efficacy/E9/Step4/E9_Guideline.pdf
- 4 CPMP. Points to Consider on Missing Data. EMEA: London, 2001. Available at https://www.ema.europa.eu/en/documents/scientific-guideline/points-consider-missing-data_en.pdf
- 5 Guidance for Industry Clinical Trial Endpoints for the Approval of Cancer Drugs and Biologics, May 2007.
- 6 Guidance for Industry ICH. *E14 Clinical Evaluation of QT/QTc Interval Prolongation and Proarrhythmic Potential for Non-Antiarrhythmic Drugs*. 12 May 2005.
- 7 SAS Institute Inc., Cary, NC, USA.

12. Appendices

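### Does the SAP's undeclared move of the primary ORR from the efficacy-evaluable to the treated population need correcting?

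*Protocol*

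**What the plan says.** Protocol Section 9.4.1 gives the default: "Unless otherwise specified, efficacy analyses will be based on the efficacy-evaluable population and will be summarized by the initial combination dose level". Within that section only PFS and OS are moved to the all-treated population, so ORR, DCR and DOR stay on efficacy-evaluable. Protocol Section 9.4 describes its own content this way: "This section is a summary of the planned statistical analyses of the primary and secondary endpoints".

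SAP Section 7.6 has the roles the other way round: "The efficacy endpoints of ORR, DCR, and DOR will be based on the treated population". It continues: "As supportive analyses, these efficacy endpoints will also be summarized for the efficacy-evaluable population". On missing response data it says that "subjects among the analysis population who have not achieved the outcome of interest by the time of analysis will be considered a non-responder".

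On precedence, SAP Section 1 says: "This SAP supersedes any statistical considerations identified in the protocol; where considerations are substantially different, they will be so identified". SAP Section 10, headed as the place for significant changes from the protocol, reads: "There have been no other changes in analyses from those defined in the protocol". SAP Section 9 adds: "Any deviations from this statistical plan will be described and justified in the final clinical study report".

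**The concern.** ORR is the only primary endpoint of an open-label, single-arm study, and its estimate and interval are the main result. The protocol and the SAP name different denominators for it. The SAP promises to flag substantial differences, and the section meant for them flags none. Its phrase about no other changes even presupposes a list that is not there. SAP Section 9 covers departures from the SAP only, so a study report that followed the SAP exactly would have no prompt to mention the switch.

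At stake is traceability. A reader comparing the protocol with the report would find a different primary denominator and no stated reason. In an open-label study, that reader might also wonder whether the denominator was chosen after results had been seen.

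**Working it through.** **1. The plan's own precision figures.** SAP Section 2.3 expects 20 to 40 subjects treated at the final expansion dose. For an observed 45% it gives one-sided 80% exact lower bounds of 33.7% and 37.3%. The exact lower bound is the Beta quantile L = B(α; x, n − x + 1).

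- n = 20, x = 9: B(0.20; 9, 12) = 33.68%
- n = 40, x = 18: B(0.20; 18, 23) = 37.34%

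Both reproduce to rounding. They are framed on the number treated.

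**2. Who differs between the populations.** Both documents define efficacy-evaluable as measurable disease at baseline, at least one dose, and one of: a post-baseline response assessment, death, or clinical progression before that assessment. A treated subject therefore drops out in one of two ways:

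- (a) alive, without clinical progression and never assessed after baseline; or
- (b) without measurable disease at baseline.

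Route (b) breaches inclusion criterion 4. Route (a) is narrowed by Protocol Sections 7.1 and 8.1, which call for an end-of-treatment visit within 30 days of the last dose and imaging at end of treatment.

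**3. Direction.** A subject lost by route (a) has no assessment and cannot be a responder. With x responders among n treated and k subjects lost this way:

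shift = x/(n − k) − x/n = [x/(n − k)] × (k/n)

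This is never negative and never exceeds k/n. The treated ORR is therefore equal to or below the efficacy-evaluable ORR.

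Route (b) could reverse this, but only if the ineligible subject is counted as a responder. One such case among 18 of 40 would give 17/39 = 43.6% on efficacy-evaluable against 45.0% on treated.

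**4. Size.** The documents give no value for k. Assume 0 to 2 at n = 40 and 0 to 1 at n = 20, that is, up to 5% of those treated. The intervals are the two-sided 95% Clopper-Pearson intervals that the SAP plans: lower B(0.025; x, n − x + 1), upper B(0.975; x + 1, n − x).

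| Treated | k | Treated ORR (95% CI) | Efficacy-evaluable ORR (95% CI) | Shift (points) |
|---|---|---|---|---|
| 18/40 | 0 | 45.0% (29.3–61.5) | 45.0% (29.3–61.5) | 0 |
| 18/40 | 1 | 45.0% (29.3–61.5) | 18/39 = 46.2% (30.1–62.8) | 1.2 |
| 18/40 | 2 | 45.0% (29.3–61.5) | 18/38 = 47.4% (31.0–64.2) | 2.4 |
| 9/20 | 0 | 45.0% (23.1–68.5) | 45.0% (23.1–68.5) | 0 |
| 9/20 | 1 | 45.0% (23.1–68.5) | 9/19 = 47.4% (24.4–71.1) | 2.4 |

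The treated intervals are 61.5 − 29.3 = 32.2 and 68.5 − 23.1 = 45.4 points wide, so these shifts are small beside the sampling error.

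**5. Other endpoints.** DCR behaves as ORR does, because an unassessed subject cannot count as disease control. DOR uses responders only, so it is the same in both populations unless a responder is lost by route (b). PFS and OS are on all treated subjects in both documents.

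**6. What a declaration would change.** Both populations are already planned for ORR, DCR and DOR. Protocol Section 9.1 and SAP Section 7.1 rule out hypothesis testing, so no error rate or power depends on the choice. Adding the sentence would alter no planned table or estimate.

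**The case for a change.** The strongest reply is that the SAP breaks its own rule. The sentence in SAP Section 1 that gives the SAP precedence also promises that substantial differences will be identified. Changing the main population of the primary endpoint is more than added detail to a protocol summary. The protocol's allowance for other specification permits the choice, but it does not make the statement in SAP Section 10 accurate. Protocol V5.0, dated 06 September 2023 and so later than the SAP of 18 April 2023, still names efficacy-evaluable. The cohort-level estimates have smaller denominators, so one subject weighs more there.

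Most of this stands as a description. SAP Section 10 is incomplete when read against the protocol supplied. Two points limit it:

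- The SAP was written on Protocol V4.0, which is not supplied. The visible V5.0 change log has no Section 9 entry, so V4.0 probably had the same wording, but that is an inference.
- The switch is not concealed. SAP Section 7.6 names both populations and the role of each, and the ORR on the protocol's population will still be reported.

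The worry about a choice made on seen data has little force either, since the SAP's choice can raise the ORR only through an ineligible subject counted as a responder.

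**Conclusion.** No change to the plan. The two documents do name different main populations for ORR, DCR and DOR, and SAP Section 10 does not say so. This is an omission of record. It is clear which analysis governs, both are planned, and the main one is normally the more conservative. The effect on the reported ORR may be zero. At an observed 45% it is 1.2 points for one non-evaluable subject among 40 treated and 2.4 points for one among 20, and it can never exceed the fraction of treated subjects who were never assessed.

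This rests on three assumptions: few treated subjects escape assessment, death and clinical progression alike; the measurable-disease criterion is respected at entry; and the report presents both populations as the SAP plans. The authors of the report can note the difference in a sentence when they present the two denominators together. The results and their interpretation do not depend on it.
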